6.4 Treatment compliance

The first single dose of AZD7648 will be taken whilst the patient is in the clinic (Cycle 0, Day 1) and the administration of this dose will be recorded in the appropriate section of the CRF.

From Cycle 1 onwards, patients will self-administer AZD7648. All patients will be required to complete a Patient Diary, which must be returned to the clinic for review at each visit. The Patient Diary will contain detailed instructions on how to take the study treatment. The patient should be instructed to record the date and time that all dose(s) of AZD7648 were taken in the Patient Diary. If a dose is missed, the reason must be noted in the Patient Diary. The emergency address and telephone number should be written on a Patient Diary and the patient will be instructed to keep this in their possession at all times. A copy of the Patient Diary is provided in the study reference materials.

Study site staff will make tablet counts at regular intervals during treatment. Compliance will be assessed by the tablet count and the information will be recorded in the appropriate section of the CRF. After the tablet count has been performed, the remaining tablets will not be returned to the patient but will be retained by the investigative site until reconciliation is completed by the study monitor. All patients must return their bottle(s) of AZD7648 at the appropriate scheduled visit, when a new bottle will be dispensed. Patients will be instructed to notify study site personnel of missed doses. Dates of missed or held doses will be recorded by the patient Diary and by the site staff on the CRF.

Patients must return all containers and any remaining tablets at the end of the study.

Any change from the dosing schedule, does interruptions, dose reductions, dose discontinuations should be recorded in the CRF.

The Investigational Product Storage Manager is responsible for managing the study treatment from receipt by the study site until the destruction or return of all unused study treatment. The Investigator(s) is responsible for ensuring that the patient has returned all unused study treatment.

6.5 Concomitant therapy

Unless clinically indicated, patients should avoid taking additional non-study medications that may interfere with the study treatments. Any medication or vaccine, including over-the-counter or prescription medicines, that the patient is receiving at the time of enrolment or receives during the study must be recorded in the CRF along with:

- Reason for use
- Dates of administration including start and end dates
- Dosage information including dose and frequency

Details of prohibited medications are detailed in Table 5 and Appendix F includes guidance regarding potential interactions with concomitant medications.

Table 5	Prohibited	medications

Prohibited medication/class of drug:	
Unless stated otherwise, these medications are prohibited from the time that patients enter the main screening period until the last dose of study treatment. The pre-screen may be done whilst on prior therapy	
Any investigational anti-cancer therapy other than those under investigation in this study	Should not be given concomitantly whilst the patient is on study treatment
Any concurrent chemotherapy, radiotherapy, immunotherapy, biologic or hormonal therapy, or any other novel agent for cancer treatment other than those under investigation in this study	Should not be given concomitantly whilst the patient is on study treatment
	Note : concurrent use of hormones for non-cancer-related conditions, eg, insulin for diabetes and stable dose of hormone replacement therapy and luteinising hormone replacement therapy analogues (> 6 months) is acceptable.
	Palliative radiotherapy may be used for the treatment of pain, provided the Investigator does not consider these are indicative of clinical progression. Study treatment should be discontinued a minimum of 3 days before a patient undergoes palliative radiotherapy, and study treatment restarted within 4 weeks (provided any bone marrow toxicity has recovered)
Herbal medications and supplements	Should not be given concomitantly unless agreed by the Sponsor. This is due to their potential to modulate CYP3A4 activity (see below and further details in Appendix F)

Prohibited medication/class of drug:	
Concomitant medications known to significantly modulate CYP3A4 activity	The principal enzyme for metabolising AZD7648 is CYP3A4. Patients should avoid concomitant medications and foods known to significantly modulate CYP3A4 activity (potent/strong inhibitors or inducers of CYP3A4). The required washout period prior to starting study treatment is 3 weeks (5 weeks for enzalutamide or phenobarbital) until 28 days after the last dose of study treatment See also Appendix F
Live virus and bacterial vaccines	Prohibited whilst the patient is receiving study treatment and during the 28-day follow-up period

Table 5Prohibited medications

6.5.1 Other concomitant treatment

Other medication other than that described above, which is considered necessary for the patient's safety and wellbeing, may be given at the discretion of the Investigator and recorded in the appropriate sections of the CRF.

If the Investigator, based on his medical judgement, feels that medications described above are essential to patient's wellbeing, such products may be administered with caution following discussion between the Investigator and the AZ Study Physician.

Patients who are taking warfarin may participate in this study; however, it is recommended that INR be monitored carefully at least once per week for the first month, then monthly if the INR is stable. Subcutaneous heparin, low molecular weight heparin, and new oral anticoagulants (NOACs) are permitted. The use of granulocyte-colony stimulating factor (G-CSF) is not permitted for primary prophylaxis or secondary prophylaxis during Cycle 0 or Cycle 1 (unless deemed by the investigator that this is essential to the patient's well-being). If required for secondary prophylaxis from Cycle 2 onwards, this should be administered following discussion between the Investigator and the AZ Study Physician.

6.5.2 Support medication

There is no antidote medication for AZD7648; restricted medications are described in Appendix F. Rescue medication for PLD in Combination Module 1 will follow the local label.

The use of rescue medications is allowable at any time during the study. The date and time of rescue medication administration as well as the name and dosage regimen of the rescue medication must be recorded in the CRF.

Concomitant medications or treatments (eg, paracetamol or diphenhydramine) deemed necessary to provide adequate prophylactic or supportive care, except for those medications identified as "prohibited," as described in Table 5), are to be administered as prescribed by the Investigator.

Best supportive care, including antibiotics, nutritional support, correction of metabolic disorders, optimal symptom control, and pain management (including palliative radiotherapy) should be used for all patients, when necessary.

Inactivated viruses, such as those in the influenza vaccine are permitted during the study.

AstraZeneca recommends avoiding administering COVID-19 vaccination for 72 hours prior to administration of the first dose of study drug, or during the dose-limiting toxicity period, to avoid biases in the interpretation of safety data due to the potential overlap of vaccine-related AEs with study drug-related AEs.

6.6 Dose modification

Details of dose escalation can be found in Section 6.1.2.

Study treatment will be repeated in 28-day cycles. The dosing criteria for Day 1 of a new cycle of study treatment (blood tests should be reviewed prior to dosing) and continuation of treatment are:

- ANC $\geq 1500 \text{ cells/mm}^3 (\geq 1.5 \text{ x } 10^9/\text{L})$
- platelets \geq 75,000/mm³ (\geq 75 x 10⁹/L)

If a patient experiences a clinically significant and/or unacceptable toxicity (including a DLT) study treatment will be interrupted (and appropriate treatment administered) for a maximum of 28 days until resolution of the toxicities to the patient's baseline or until improvement (CTCAE Grade ≤ 2) (Table 6). Clinically significant abnormal laboratory values must be repeated at regular intervals until resolved to the patient's baseline or until improvement (CTCAE Grade ≤ 2). If the patient is showing clinical benefit and the toxicity resolves to the patient's baseline or until improvement (CTCAE Grade ≤ 2). If the patient (CTCAE Grade ≤ 2), treatment can be restarted; guidelines are provided below for dose modifications (Table 7).

If the toxicity does not resolve to the patient's baseline or to CTCAE Grade ≤ 2 within 28 days of onset, treatment with AZD7648 must be discontinued.

Event (CTCAE V5.0)	Action
Grade 1 to 2 toxicity (all events)	Investigator judgement to continue treatment or interrupt dose (maximum 28 days), except for Day 1 of a new cycle of study treatment, as described above. Initiate optimal supportive care and causality investigation. Consider resuming at the same dose level when toxicity has resolved or is resolving with prophylactic treatment (if appropriate). If toxicity recurs on rechallenge and does not resolve in < 7 days despite optimal supportive care, consider a dose reduction.
Grade 3 to 4 toxicity (1 st event)	Interrupt study treatment, initiate optimal supportive care and causality investigation. Maximum treatment interruption is 28 days. When toxicity has resolved or is resolving with prophylactic treatment (Grade ≤ 2 or returns to baseline), consider re-starting AZD7648 with 1 dose level reduction and prophylactic treatment (if appropriate).
Grade 3 toxicity (recurrence of same AE)	Interrupt study treatment, initiate optimal supportive care and causality investigation. Maximum treatment interruption is 28 days. When toxicity has resolved or is resolving (Grade ≤ 2 or returns to baseline), consider re- starting AZD7648 with 1 dose reduction and prophylactic treatment (if appropriate). After 2 dose reductions, consider permanent discontinuations of AZD7648 for Grade 3 events.
Grade 4 toxicity (recurrence of same AE)	Patients should permanently discontinue AZD7648.

Table 6 Management of AZD7648 treatment related toxicity

Table 7Dose modification of study treatment AZD7648

First dose reduction	Previously determined "acceptable safety" dose level.
Second dose reduction	Previously determined "acceptable safety" dose level.
Third dose reduction	Consider permanent discontinuation of AZD7648 unless the patient is deriving clinical benefit.

Patients enrolled into the first 3 dose cohorts are permitted to dose reduce to the previous dose cohort, but must discontinue if a dose reduction is required in the first dose level.

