6.1.3 Definition of dose-limiting toxicity

DLTs will be evaluated during Cycle 0 and Cycle 1 of treatment. Toxicity will be graded according to the National Cancer Institute CTCAE v5.0.

A DLT is defined as an AE that occurs from the first dose of study treatment up to and including Cycle 1, Day 28 (the DLT assessment period) that is assessed as unrelated to the disease, intercurrent illness, or concomitant medications and that, despite optimal therapeutic interventions, meets any of the following criteria:

Haematological Toxicities:

- Grade 4 neutropenia lasting > 4 days.
- Grade 4 thrombocytopenia.
- Grade \geq 3 neutropenia (ANC < 1000 cells/mm³ [< 1 x 10⁹/L]) of any duration accompanied by fever \geq 38.5°C and/or systemic infection.
- Grade \geq 3 thrombocytopenia (< 50,000/mm³ [< 50 x 10⁹/L]) with bleeding.

Non-haematological Toxicity CTCAE Grade ≥3 Including:

- Confirmed laboratory abnormalities greater than 72 hours of duration.
- Nausea or vomiting for more than 3 consecutive days despite administration of maximal anti-emetic therapy.
- Diarrhoea for more than 3 consecutive days despite administration of maximal anti-diarrhoeal therapy.
- QTc prolongation > 500 milliseconds or QTcF prolongation from baseline by 60 milliseconds confirmed on at least 2 separate ECGs.
- Any other toxicity that is greater than that at baseline AND is clinically significant and/or unacceptable, and does not respond to optimal therapeutic intervention within 72 hours AND is judged to be a DLT by the SRC.
- Any treatment-related event, including significant dose reductions, omissions or delays, judged to be a DLT by the SRC. Examples may include CTCAE Grade 2 toxicities that are clinically significant and/or unacceptable according to the Investigator, toxicities that result in an inability to administer at least 75% of study treatment during Cycle 1 or delay the administration of study treatment in the subsequent cycle by ≥ 7 consecutive days.

DLT Will not Include the Following:

- Transient isolated laboratory abnormalities which are not considered clinically significant and resolve to baseline within 72 hours without any intervention.
- Alopecia.
- Toxicity unrelated to treatment eg, related to the underlying disease or disease-related process under investigation.
- Grade 4 vomiting and diarrhoea lasting < 72 hours in the absence of maximal medical therapy.

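### For a Grade 2 toxicity judged unacceptable or a DLT, the Section 6.6 text requires interruption while Table 6 allows dosing to continue, and the Grade ≤ 2 thresholds do not work for an event that stays at Grade 2

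*Protocol*

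**What the plan says.** Protocol Section 6.1.3 describes the events that the SRC may judge dose limiting: "Examples may include CTCAE Grade 2 toxicities that are clinically significant and/or unacceptable according to the Investigator".

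Section 6.6 uses the same description and names DLTs: "If a patient experiences a clinically significant and/or unacceptable toxicity (including a DLT) study treatment will be interrupted". The sentence sets no grade limit and caps the interruption at 28 days. It ends the interruption at the patient's baseline or on improvement to Grade 2 or below, and it refers to Table 6.

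The first row of Table 6 is labelled "Grade 1 to 2 toxicity (all events" and its action begins "Investigator judgement to continue treatment or interrupt dose (maximum 28 days". The row's one exception is Day 1 of a new cycle. On resumption it says: "Consider resuming at the same dose level when toxicity has resolved or is resolving with prophylactic treatment".

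The Section 6.6 text has its own restart condition: "If the patient is showing clinical benefit and the toxicity resolves to the patient's baseline or until improvement (CTCAE Grade ≤ 2". Its stopping rule takes effect "If the toxicity does not resolve to the patient's baseline or to CTCAE Grade ≤ 2 within 28 days of onset". Section 7.1 gives the same limit as an example of an adverse-event reason for discontinuing. Section 14.4 repeats it for Combination Module 1, where it covers both drugs.

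**The concern.** Two instructions cover the same event. The text makes interruption mandatory, and the table that the text cites makes it discretionary. Section 8.4.5 sends the reader to Section 6.6 for details of DLTs, so this is where a site would look.

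The first thing at stake is whether a patient in a first-in-human escalation keeps taking the drug during an event serious enough to be called dose limiting. The second is whether sites deliver Cycle 1 dosing in the same way.

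The thresholds add a further difficulty. A Grade 2 event can be dose limiting under Section 6.1.3 and yet sit within the recovery limit of Sections 6.6, 7.1 and 14.4. The protocol does not treat Grade 2 as resolved everywhere: Section 7.1 has patients who withdraw for treatment-related toxicity observed until Grade 1 or below, or baseline.

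**Working it through.** The plan gives no figure to reproduce, so the check is to apply each rule to one test case. Take a treatment-related, non-haematological toxicity that starts at Grade 2 from a lower baseline and stays at Grade 2. The investigator calls it unacceptable and the SRC judges it a DLT.

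1. **Section 6.1.3.** The event can be a DLT.
2. **Section 6.6 text.** Treatment is interrupted, for at most 28 days.
3. **Table 6, Grade 1 to 2 row.** The investigator may continue treatment, which is an interruption of 0 days, or interrupt for at most 28 days. DLTs are not excepted.
4. **Steps 2 and 3 together.** Interruption is both required and optional. The permitted range across the two passages is 0 to 28 days.
5. **Restart.** The grade part asks for Grade ≤ 2. Since 2 ≤ 2, it is met on the day of onset. The text also asks for clinical benefit. If its word improvement means a fall in grade, an unchanged Grade 2 event fails. Table 6 asks instead whether the toxicity has resolved or is resolving, and a constant event meets neither. The tests give different answers for the same patient.
6. **28-day stop.** It applies only if the toxicity is still above Grade 2 and above baseline at 28 days. Since 2 > 2 is false, the rule is not triggered while the event stays at Grade 2. Sections 7.1 and 14.4 give the same result.
7. **Reaching the cap.** The Grade 1 to 2 row limits interruption to 28 days but does not say what follows if the event is still at Grade 2 by then.
8. **Comparison case.** For a first Grade 3 to 4 event, text and table both say interrupt. The conflict over interruption is confined to the low-grade row.

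Nothing here rests on the exact punctuation of the restart sentence.

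**The case against.** The best reply is that text and table can be read together. The text is triggered by a judgement that the toxicity is clinically significant or unacceptable, which Section 6.1.3 leaves to the investigator at Grade 2. The table also leaves the action to the investigator. One who finds the event unacceptable interrupts; one who does not may continue. The SRC's label may also come after the site has managed the event: Section 6.1.2 has the SRC evaluate patients once the DLT period is complete, and SAP Section 3.2.1.3 takes DLTs as the SRC documents them.

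This removes part of the conflict. It does not help once the event has been called unacceptable. The text's trigger needs no SRC ruling, the table row still permits continuation, and no passage says which prevails.

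On the thresholds, a mandatory stop limited to toxicity above Grade 2 may be deliberate. Section 7.1 also allows discontinuation by patient or investigator decision and for unacceptable risk. An event that worsens to Grade 3 moves to another row. Separate neutrophil and platelet criteria can still hold dosing. All of this stands, and it limits what can be claimed.

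A reader might infer four stronger things that the documents do not support:

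- **The interruption is open-ended.** Both text and table cap it at 28 days.
- **Such a patient can never be stopped.** The 28-day rule fails only while the event stays at Grade 2, and other stopping routes exist.
- **Resuming at the same dose level contradicts the text.** The text sets no restart dose and points to Table 7 for guidance.
- **One Grade 2 DLT in a small cohort measures the harm to the maximum tolerated dose (MTD) estimate.** The DLT is counted once whether or not dosing continues, and the MTD comes from a model fitted to cumulative data.

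**Conclusion.** The point holds. For a Grade 2 event called unacceptable or a DLT, the Section 6.6 text and Table 6 give incompatible instructions, from no interruption to up to 28 days. The grade part of the restart and 28-day rules is already satisfied by an event that stays at Grade 2, so these thresholds do no work for it.

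This rests on reading the table row as written, with no unstated exception for DLTs, and on non-haematological events.

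The effect on the results cannot be sized, because the documents give no frequency for Grade 2 DLTs. One indirect route to the DLT data exists, for an event that is interrupted but not yet judged a DLT. On a continuous 28-day schedule with equal daily doses (an assumption), 28 × 25% = 7 days. Missing more than 7 days takes delivery below the 75% of planned Cycle 1 dose that Section 6.1.2 uses for evaluability and Section 6.1.3 gives as a DLT example. How often that would happen is unknown. The main reason to act is patient safety and consistent conduct across sites.

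**What to change.** Reconcile Section 6.1.3, the Section 6.6 text, Table 6, Section 7.1 and Section 14.4. Text and table should give one instruction for a Grade 2 event judged unacceptable or a DLT, covering interruption, restart and the 28-day rule. The sponsor's clinicians decide what that instruction is.

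The cost is wording only, with no new data or patients. SAP version 4.0 (Section 1.1) records that development was halted, so a written clarification may be more proportionate than a full amendment. It still has a use, because protocol Section 4.4 lets patients who benefit continue treatment after the final data cut-off. The study report can also state how any DLT declared at Grade 2 was managed.

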6.7 Treatment after the end of the study

Patients are permitted to either receive standard of care therapy, or to continue to receive study treatment following the end of the study if, in the opinion of the Investigator, they are continuing to receive benefit from treatment. After discontinuation of study treatment, the Investigator will be at liberty to define further the most appropriate anti-cancer treatment. Subsequent anti-cancer treatment is expected to be initiated following the cancer recurrence or development of a new cancer. Information on subsequent anti-cancer therapies should be recorded on the clinical database.

7 PATIENT DISCONTINUATION OF TREATMENT AND PATIENT WITHDRAWAL

7.1 Discontinuation of study treatment

Patients may be discontinued from study treatment in the following situations. Note that discontinuation from study treatment is NOT the same as a complete withdrawal from the study:

- Disease progression (confirmed progression or symptomatic deterioration or confirmed progression by RECIST criteria).
- Adverse event, eg, study treatment-related toxicity that fail to recover to CTCAE Grade ≤2 or the patient's baseline within 28 days. Patients that withdraw due to treatment-related toxicity must be observed until resolution of toxicity to CTCAE Grade ≤1 or the patient's baseline.
- Patient or Investigator decision. The patient is at any time free to discontinue treatment, without prejudice to further treatment.
- Pregnancy.
- Non-compliance with the CSP (Investigator or patient).
- Patients incorrectly initiated on study treatment.
- Unexpected, significant or unacceptable risk to the patients enrolled in the study.
- Lack of evaluable and/or complete data.
- Decision to modify the development plan of the drug.
- Sponsor termination of study due to unfavourable risk-benefit.

See the SoA for data to be collected at the time of treatment discontinuation and follow-up and for any further evaluations that need to be completed.

7.1.1 Temporary discontinuation

See Section 6.6 for further details on study treatment interruptions.

7.1.2 Rechallenge

See Section 6.6 for further details on study treatment interruptions.

7.1.3 **Procedures for discontinuation of study treatment**

The Investigator should instruct the patient to contact the site before or at the time if study treatment is stopped. A patient that decides to discontinue study treatment will always be asked about the reason(s) and the presence of any AEs. The date of last intake of study treatment should be documented in the CRF. All study treatment should be returned by the patient at their next on-site study visit or unscheduled visit. Patients permanently

discontinuing study treatment should be given locally available standard of care therapy, at the discretion of the Investigator.

Discontinuation of study treatment, for any reason, does not impact on the patient's participation in the study. The patient should continue attending subsequent study visits and data collection should continue according to the study protocol. If the patient does not agree to continue in-person study visits, a modified follow-up must be arranged to ensure the collection of endpoints and safety information. This could be a telephone contact with the patient, a contact with a relative or treating physician, or information from medical records. The approach taken should be recorded in the medical records. A patient that agrees to modified follow-up is not considered to have withdrawn consent or to have withdrawn from the study.

